13.5. ANALYSIS OF SAFETY

Safety analyses will be conducted on the ITT population and included the incidence of adverse events and serious adverse events.

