11. STUDY SCHEDULE

11.1. Procedures at Each Visit

Screening and Baseline Visit – within 30 days of onset of TBI (Study Day 0)

- Neurological and physical exam
- Hematology and blood chemistry
- Demographic data
- Medical history
- Concomittant Medication
- Evaluation Scales
 - Processing Speed Index
 - Stroop Color-Word Test
 - Trail Making Test
 - Digit Span
 - Montreal Cognitive Assessment
 - Hamilton Anxiety Rating Scale
 - Hamilton Rating Scale for Depression
 - One Touch Stockings of Cambridge
 - Multitasking Test
 - Reaction Time
- ET

Date: 040418

STUDY ID: CAPTAIN - rTMS

Scales

Scales

qEEG

Treatment cycles

Each patient shall receive three cycles of treatment of 10 infusions on 10 consecutive days

- Study days 31-40,
- Study days 61-70
- Study days 91-100

Visit 1 – Efficacy Evaluation (study day 101)

- Neurological and Physical exam
- Evaluation
 - Processing Speed Index
 - Stroop Color-Word Test
 - Trail Making Test
 - Digit Span
 - Montreal Cognitive Assessment
 - Hamilton Anxiety Rating Scale
 - Hamilton Rating Scale for Depression
 - One Touch Stockings of Cambridge
 - Multitasking Test (MTT)
 - Reaction Time
- ET
- qEEG

Visit 2 – Efficacy Evaluation (study day 180)

- Neurological and Physical exam
- Evaluation
 - Processing Speed Index

Date: 040418

- Stroop Color-Word TestTrail Making Test
- Digit Span
- Montreal Cognitive Assessment (
- Hamilton Anxiety Rating Scale
- Hamilton Rating Scale for Depression
- One Touch Stockings of Cambridge
- Multitasking Test (MTT)
- Reaction Time
- ET
- qEEG

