13.13.2. Safety Population

Safety population includes all patients who have had at least one dose of study medication and one contact with the Investigator afterwards. It will be used for safety analysis.

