13.13.3. ITT Population (Full Analysis Set)

ITT population is defined as all patients who have no "severe" violation of entry criteria, had at least one dose of medication and at least one post-baseline observation of at least one primary efficacy criterion ("modified" ITT). This way ITT is defined in the sense of the "full analysis set" according to ICH E9 § 5.2. ("Analysis Sets") . ITT population will be used for all efficacy analyses.

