10. ANALYSIS SETS

ITT population will be used for all efficacy analyses. ITT population is defined as all patients who have no "severe" violation of entry criteria, had at least one dose of medication and at least one post-baseline observation of at least one primary efficacy criterion ("modified" ITT). This way ITT is defined in the sense of the "full analysis set" according to ICH E9 § 5.2. ("Analysis Sets").

A sensitivity analysis will be performed for a per protocol (PP) data set as an exploratory approach. The PP population includes all patients who are eligible for ITT evaluation and who additionally do not show major protocol deviations. The supportive analysis by means of the per-protocol set will be regarded as of equal scientific importance as the ITT analysis, since it most closely reflects the scientific model underlying the protocol (see ICH E9, section 5.2.2).

Safety population includes all patients who have had at least one dose of study medication and one contact with the Investigator afterwards. It will be used for safety analysis.

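### SAP 13.5 puts the safety analyses on the modified ITT set, contradicting SAP 10 and Protocol 13.13.2; if followed, it can drop exposed patients from the adverse event tables

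*SAP*

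**What the plan says.** The SAP gives two different populations for the same analysis.

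- SAP 13.5, the section on safety analysis: "Safety analyses will be conducted on the ITT population and included the incidence of adverse events and serious adverse events".
- SAP 10, the section on analysis sets: "Safety population includes all patients who have had at least one dose of study medication and one contact with the Investigator afterwards". The next sentence assigns that set to safety analysis.
- Protocol 13.13.2 defines the Safety population in the same way and says of it: "It will be used for safety analysis".
- Protocol 13.13.3 gives the ITT set a different job: "ITT population will be used for all efficacy analyses". SAP 10 agrees.

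Both documents describe the ITT set as a modified one. A patient must have no 'severe' violation of the entry criteria and, in the words of SAP 10, must have "had at least one dose of medication and at least one post-baseline observation of at least one primary efficacy criterion".

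The first post-baseline efficacy assessment is Visit 1, listed in Protocol 11.1 as "Efficacy Evaluation (study day 101"). SAP 7 adds a window of 7 days either side. Treatment cycles run on days 31-40, 61-70 and 91-100 (Protocol 11.1, SAP 7 and SAP 13.3).

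**The concern.** A safety denominator should include everyone exposed, whatever happens to them afterwards. The ITT set does not: membership depends partly on reaching an efficacy test, and the first such test is scheduled after the last treatment day. A patient withdrawn early for a serious adverse drug reaction, which is one of the listed withdrawal reasons (Protocol 6.3.2, SAP 13.1), may never be tested and would then be missing from the analysis meant to describe tolerability. Loss of this kind can also differ between arms, so comparisons as well as rates could be affected.

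The safety of rTMS is a stated secondary objective and rTMS adverse events are a secondary endpoint (SAP 5.2 and 8.2). Protocol 3.1 names seizure induction as the main area of concern for TMS in stroke or TBI patients, while adding that it has rarely been reported. With 30 patients on active rTMS, a single missing patient matters. SAP 13.5 is also the only place where the SAP says which safety results will be produced, so a programmer could reasonably follow it.

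**Working it through.** The plan states no figure that could be reproduced here. The check compares the definitions and then counts.

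**1. Who is in one set but not the other.** Both sets require at least one dose. The Safety set adds one later contact with the investigator. The ITT set adds no 'severe' entry violation and one post-baseline observation of any one primary criterion. Patients in the Safety set but outside the ITT set are therefore:

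- (a) dosed patients seen again by the investigator but with no post-baseline efficacy observation;
- (b) dosed patients seen again but with a 'severe' entry violation.

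**2. How much exposure can precede the first efficacy observation.** Planned treatment days: 3 cycles × 10 = 30.

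| Visit 1 on | Days since day 31 | Planned treatment days before the visit |
|---|---|---|
| day 94 (window opens) | 94 − 31 = 63 | 10 + 10 + 3 = 23 of 30 |
| day 101 (nominal) | 101 − 31 = 70 | 30 of 30 |
| day 108 (window closes) | 108 − 31 = 77 | 30 of 30 |

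A patient can thus receive most or all of the course and still fall into group (a). Neither schedule (Protocol 11.1, SAP 7) includes an early-termination efficacy visit. These counts use the schedule sections as they stand. Protocol 7.1.1 gives days 32-40 for the first cycle, a separate inconsistency that the sponsor must reconcile and that does not affect this point.

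**3. Effect on a reported rate.** Let *n* be the Safety set in one arm, *m* the number excluded from ITT, *e* the excluded patients with an event, and *l* the retained patients with an event.

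- Safety set rate = (*e* + *l*)/*n*
- ITT rate = *l*/(*n* − *m*)

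The ITT rate is the lower of the two exactly when *e*/*m* > (*e* + *l*)/*n*, that is, when events are more frequent among the excluded than overall.

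Hypothetical counts for one arm with *n* = 30:

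| *m* | *e* | *l* | Safety set | ITT set |
|---|---|---|---|---|
| 1 | 1 | 0 | 1/30 = 3.3% | 0/29 = 0% |
| 3 | 3 | 0 | 3/30 = 10% | 0/27 = 0% |
| 3 | 3 | 2 | 5/30 = 16.7% | 2/27 = 7.4% |
| 3 | 0 | 2 | 2/30 = 6.7% | 2/27 = 7.4% |

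The last row shows that the direction is not guaranteed: if the excluded patients left for unrelated reasons, the ITT rate rises slightly.

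**4. How many patients might be affected.** The documents give no rate of loss before Visit 1. If 0%, 5%, 10% or 20% of 90 patients were dosed and then lost without an efficacy observation, the numbers would be 0, 4 to 5, 9 or 18. The 10% in Protocol 13.9 is a general sample-size allowance for dropouts and similar problems; it is not an estimate of this quantity.

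**The case against.** The strongest reply is that the right set is already defined and assigned, in SAP 10 and in the protocol, so 13.5 may be no more than a slip. That is fair as to intent. But nothing says which sentence governs, and 13.5 is the section that describes the safety output. What stands is that the loss happens only if 13.5 is followed.

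Three stronger readings are tempting, and the documents do not support them.

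- **A reader might infer that any patient who stops treatment for an adverse event before day 101 is dropped.** Stopping treatment is not leaving the study. Compliance below 80% removes a patient from the per-protocol set only (Protocol 13.15, SAP 13.3). Reasonable effort is to be made to complete assessments even in patients lost to follow-up (Protocol 6.3.2, SAP 13.1), and one observation on one primary criterion is enough for ITT. Nor is day 101 a hard cut-off, since the SAP window opens at day 94.
- **A reader might infer that early events and withdrawals disappear.** They do not. All adverse events are documented, the withdrawal page records date, initiator and reason, and serious adverse reactions go to the sponsor within 24 hours (Protocol 6.3.2, 10.5 and 10.6). What is at risk is the incidence analysis, not the record.
- **A reader might infer that deaths before Visit 1 are certainly excluded.** Protocol 13.12 plans worst-rank scores for patients who cannot be tested for TBI-related reasons and prefers to keep deaths in the descriptive statistics. That sits awkwardly with an ITT definition that asks for an observation, and SAP 12.1 keeps the missing-data codes without restating the imputation. Their status is unclear.

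**Conclusion.** SAP 13.5 is wrong as written. It contradicts SAP 10 and Protocol 13.13.2, and neither document gives a reason for departing from the Safety population. If 13.5 governs, exposed patients with no post-baseline efficacy observation, and exposed patients with a 'severe' entry violation, are left out of the adverse event and serious adverse event incidence tables. The first exclusion depends on what happens after dosing. It would most plausibly lower reported rates, on the assumption that patients who leave untested have more events than those who stay.

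The size is unknown. The fall from 10% to 0% assumes that three patients in one arm all left untested because of adverse events and that nobody else in the arm had an event. It shows how sensitive arms of 30 are and is not a forecast. The primary efficacy analysis, sample size, power and alpha are unaffected.

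**What to change.** In SAP 13.5, replace the ITT population with the Safety population as defined in section 10. This brings 13.5 into line with SAP 10 and Protocol 13.13.2. The cost is one sentence; no new data are needed and no design figure changes.

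Two optional additions would help but are not needed to resolve the contradiction. The first is to state that patients are analysed by treatment received, which neither document specifies. The second is to list dosed patients who are outside the ITT set, with their events and withdrawal reasons. Because the Safety population itself requires one later contact with the investigator, such a list would also show any dosed patient whom that definition leaves out.
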